	Version: 2.0, 12SEP2021
	Page: 4 of 131

1.3 SPONSOR APPROVAL.

	Job title	DocuSign Stamp
Head of Global Clinical Operations	Senior Director Global Clinical Affairs	DocuSigned by: [name] Signer Name: [name] Signing Reason: I approve this document Signing Time: 13-Oct-2021 11:53:56 BST A32F12A80F1B4490986E80ACCB7471CB
Head of Global Clinical Strategy	Senior Director Global Clinical Strategies	DocuSigned by: [name] Signing Reason: I approve this document Signing Time: 14-Oct-2021 12:23:51 BST C809EF989A504C77BC7277E0F8E14B1D
Head of Global Biostatistics	Senior Director Global Data Analytics	DocuSigned by: Comparison of the Comparison o
Medical Affairs Representative	Vice President, Medical Affairs	DocuSigned by: July

Study Protocol	Smith-Nephew
A prospective, study to evaluate the safety and performance of PICO 14 in the management of acute and chronic wounds	Number: PICO14.WND.PRO.2019.03
	Version: 2.0, 12SEP2021
	Page: 5 of 131

2. SYNOPSIS.

Title of Study:	A prospective study to evaluate the safety and performance of PICO 14 in the management of acute and chronic wounds.	
Study Design:	ProspectiveMulti-centreNon-randomised	
Study Type:	Prospective, non-random, non-blinded case series.	
Study Product:	PICO 14.	
Comparison Group(s)*: (*if applicable)	There is no comparison group in this study.	
Study Purpose:	To generate evidence of the safe and effective use of the device in the management of chronic open wounds (pressure ulcers, venous leg ulcers, diabetes-related foot ulcers), dehisced surgical wounds and closed surgical incisions. The study comprises the PMCF for a new variant of an established product.	
Primary Objective:	To assess the functional performance of PICO 14 through verification of delivery of negative pressure and wound exudate management.	
	Closed incisions ONLY:	
	To assess clinical performance and safety of the PICO 14 NPWT system within 30 days of surgery through: • Incidence of Surgical Site Infection (SSI) – Superficial,	
Secondary Objective(s):	 Incidence of Surgical site Complications (SSC) [as applicable: dehiscence (superficial/deep etc.), seroma, necrosis, hematoma, suture abscess]. Condition of peri-wound skin assessed through visual inspection at 7, 14 and 30 days. Patient tolerability assessed by level of pain and level of satisfaction. 	

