Closed Incisions ONLY:

- Subject has a suitable, closed surgical incision which the clinician considers is suitable for PICO therapy, where it is expected that the therapy will be applied for up to 14 days.
- Any closed surgical incision in a patient in which the patient is deemed high risk of developing SSI in the opinion of the investigator.

Chronic wounds ONLY:

 Patients with any chronic wound* which the treating clinician deems is suitable for management with single-use disposable NPWT where it is expected that the therapy will applied for up to 28 days.

*Chronic wound in this study is defined as any wound of less than three months duration that is not healing after 4 weeks of standard care and having addressed the underlying cause.

Dehisced surgical wounds ONLY:

 Patients with dehisced wounds in which the clinician believes is suitable for PICO therapy where therapy is expected to be applied for up to 28 days.

*Wound dehiscence is a surgical complication in which two sides of a surgical incision separate and rupture along the incision, dehiscence typically is diagnosed after 2-3 days post-surgery and up to a month with more complicated surgeries (58). Please note the pathway to recruiting participants with dehisced wounds has changed to widen the recruitment reach. This does mean that participants seen in the community for dehisced wound will be eligible to join study, the sites will be able to screen for participants using both pathways, whether seen in clinic by surgeon in charge or in the community.

Study Protocol	Smith-Nephew
A prospective, study to evaluate the safety and performance of PICO 14 in the management of acute	Number: PICO14.WND.PRO.2019.03
and chronic wounds	Version: 2.0, 12SEP2021 Page: 8 of 131

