The most common wound-site complications are dehiscence, haematoma, seroma and surgical site infections (SSIs) (**Figure 4.2-1**, below). These are often interconnected, potentially serious complications can result in delayed or poor quality healing. Dehiscence, when a wound bursts open, can have multiple causes such as overtight closure of the wound edges, over use of the wound area leading to failure of the closure method and infection. Haematoma is a complication involving a collection of blood and fluid beneath the suture line/wound closure, which may force the wound to open up/dehisce. Seromas, common after breast mastectomy and some other types of surgery, are pockets of clear serous fluid that may persist until resorbed by the body. Sometimes, calcified tissue forms.

[figure not shown]

Figure 4.2-1: Relationships between surgical site complications

In respect of SSIs, the important clinical features are peri-incisional erythema, serous or purulent exudate and superficial dehiscence, which may be accompanied by systemic signs⁴³. They can

CONFIDENTIAL AND PROPRIETARY

Study Protocol—Device	Smith-Nephew
and performance of PICO 14 in the	Number: PICO14.WND.PRO.2019.03
	Version: 2.0, 12Sep2021
	Page: Page 26 of 131

be classified as superficial incisional, deep incisional or organ/space infections and are applicable to all types of surgery⁴⁴. For a small number of patients, SSI may progress beyond a superficial wound infection to a deep incisional or organ/space infection and affect grafts and prostheses.

PICO use in chronic wounds.

Chronic wounds are defined as wounds which are characterised by either delayed healing (typically more than 6-12 weeks) or by wounds which do not heal at all. In the US alone, an estimated 4.5 million people have chronic wounds108. Wounds can become chronic for a number of reasons; often they are stalled in the inflammatory stage of the healing process and the presence of elevated levels of matrix metallo-proteases (MMPs) as an underlying cause of wound chronicity has recently been identified.

Although commonly grouped together, chronic wounds are more correctly defined and treated according to their underlying aetiology.

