Monitor will check that site personnel are following the proper procedures for accountability and completing all necessary documentation.

7. SUBJECT ENROLLMENT AND WITHDRAWAL.

7.1 SUBJECT POPULATION.

Seventy patients with Chronic open wounds (pressure ulcers, venous leg ulcers, diabetes-related foot ulcers, dehisced surgical wounds) and Closed surgical incisions, will be recruited to the study and will receive therapy with PICO 14. There will be a minimum of 10 of each of the following wound type; venous leg ulcers, diabetes-related foot ulcers, pressure ulcers, dehisced surgical wounds and post-operative incisions. The patients will be recruited from up to 7 sites in the United Kingdom, EU, and US, Canada. Sites failing to enroll may be replaced.

7.2 INCLUSION CRITERIA.

Subjects will be considered qualified for enrollment if they meet the following criteria:

- 1. The subject must provide written informed consent.
- 2. Subjects eighteen (18) years of age or older.
- 3. Willing and able to make all required study visits.
- 4. Able to follow instructions.

Study Protocol—Device	Smith-Nephew
and performance of PICO 14 in the	Number: PICO14.WND.PRO.2019.03
	Version: 2.0, 12Sep2021
	Page: Page 43 of 131

5. Closed Incision wounds ONLY:

- Subject has a closed surgical incision which the clinician considers is suitable for PICO therapy, where it is expected that the therapy will be applied for a minimum of 14 days.
- Subject has a closed surgical incision which the clinician is deemed high risk of developing SSI.

Risk factors for surgical site infection

Patient-related	Surgery-related
Age (> 65 years)	Wound classification
Diabetes	Site and complexity of the
Obesity	procedure
Cigarette smoking	Repeat operations
Underlying illness e.g. COPD, renal insufficiency	Emergency operations
Nutritional status	
Radiation or chemotherapy exposure	
Compromised immunity, such as high dose steroid therapy	

Chronic wounds ONLY:

- Patients with any chronic wound* which the treating clinician deems is suitable for management with single-use disposable NPWT where it is expected that the therapy will applied for a minimum of 28 days.
- *Chronic wound in this study is defined as any wound of less than three months duration that is not healing after 4 weeks of standard care and having addressed the underlying cause.

Dehisced surgical wounds ONLY:

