10.4.1 SURGICAL DETAILS FOR DEHISCHED WOUNDS ONLY

Surgery details to be collected include the following questions:

- Date of surgical procedure (DD/MMM/YYYY).
- Collect surgery data [e.g. Type of surgery (type of surgery, method of closure and reference wound type and anatomical site).
- Collect surgery risk factors (elective/emergency surgery, laparoscopic (y/n), incision length, use of prophylactic antibiotics, type (single / double / triple agent) and when administered (prior to start of surgery/after surgery began), shaving of incision (yes / no / not needed), use of an incision drape (yes / no), clean/contaminated surgery (clean/clean-contaminated/contaminated/dirty), intraoperative warming (yes / no)).

10.4.2 WOUND ASSESSMENT.

Reference Wound Details Recorded at Initial Assessment

- Location of wound:
 - Upper leg;
 - lower leg;
 - o knee;
 - ankle;
- Duration of wound (weeks/months/years)
- Previous Treatment (add options given in CRF)

CONFIDENTIAL AND PROPRIETARY

Study Protocol—Device	Smith-Nephew
and performance of PICO 14 in the	Number:
	PICO14.WND.PRO.2019.03
	Version: 2.0, 12Sep2021
	Page: Page 86 of 131

- Has the reference wound been debrided? (Yes/No), if yes how?
- Has the reference wound been cleansed? (Yes/No. If yes, give detail of cleanser used).
- Reference wound measurement taken using the longest length, and width at right angles at midway point of length:
 - Length (cm);
 - Width (cm);
 - o Depth (mm)
- Appearance of the reference wound using a Modified Bates-Jensen Wound Assessment Tool:
 - Necrotic Tissue Type: Pick the type of necrotic tissue that is predominant in the wound according to colour, consistency, and adherence using this guide:

White/grey non-viable tissue	=	May appear prior to wound opening; skin surface is white or grey.
Non-adherent, yellow slough	=	Thin, mucinous substance; scattered throughout wound bed; easily separated from wound tissue.
Loosely adherent, yellow slough	=	Thick, stringy, clumps of debris; attached to wound tissue.
Adherent, soft, black eschar	=	Soggy tissue; strongly attached to tissue in centre or base of wound.
Firmly adherent, hard/black eschar	=	Firm, crusty tissue; strongly attached to wound base and edges (like a hard scab).

- None visible
- < 25% of wound bed covered

- 25% to 50% of wound covered
- 50% and < 75% of wound covered
- 75% to 100% of wound covered

CONFIDENTIAL AND PROPRIETARY

Study Protocol—Device	Smith-Nephew

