Based on data and assumptions used for sample size estimation (mean=-80.2mmHg, SD=14.8), a minimum of 55 subjects are required to achieve 80% power to detect equivalence at the significance level of α = 0.025 within

CONFIDENTIAL AND PROPRIETARY

Study Protocol—Device	Smith-Nephew
and performance of PICO 14 in the	Number: PICO14.WND.PRO.2019.03
	Version: 2.0, 12Sep2021
	Page: Page 102 of 131

6mmHg using a two one-sided t-test (TOST) approach. Drawing from past experience, it is expected that approximately 20% of the subjects may be lost to follow up by the end of the study and therefore to account for this N=70 subjects will be recruited into this study. This will allow for a minimum of 10 subjects with each of the following indications to be recruited: Chronic open wounds (pressure ulcers, venous leg ulcers and diabetes-related foot ulcers), dehisced surgical wounds and closed surgical incisions (post-operative incisions following hip or knee arthroplasty).

The sample size was estimated using SAS V9.4.

12. ADVERSE EVENTS AND DEVICE DEFICIENCIES.

12.1 DEFINITIONS.

The categories of adverse events are shown in table 12.1-1. The definitions for each of these categories are given in the subsequent sections. Table

12.1-1: Categories of Adverse Event

	NOT DEVICE-RELATED	DEVICE- OR PROCEDURE- RELATED	
Non-Serious	Adverse Event (AE)	Adverse Device Effect (ADE)	
Serious	Serious Adverse Event (SAE)	Serious Adverse Device Effect (SADE) (See 12.1.3)	
		Anticipated	Unanticipated
		Anticipated Serious Adverse Device Effect (ASADE)	Unanticipated Serious Adverse Device Effect (USADE)

CONFIDENTIAL AND PROPRIETARY

Study Protocol—Device	Smith-Nephew
and performance of PICO 14 in the	Number: PICO14.WND.PRO.2019.03
	Version: 2.0, 12Sep2021
	Page: Page 103 of 131

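### The synopsis and Section 7.2 cap a chronic wound at under three months, Section 4.2 describes it by a 6-12 week floor with no cap, and the purpose and claims state no age limit

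*Combined protocol and SAP*

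**What the plan says.** The synopsis (Section 2, inclusion criteria) and Section 7.2 carry the same footnote to the chronic-wound criterion. It fixes the meaning of the term for this study: "any wound of less than three months duration that is not healing after 4 weeks of standard care". The underlying cause must also have been dealt with. Neither these sections nor the exclusion criteria in Section 7.3 make an exception for older ulcers. The amendment log in Section 19.1.4 records added text for dehisced wounds but no change to this definition.

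Section 4.2, under the heading on PICO use in chronic wounds, describes them as "characterised by either delayed healing (typically more than 6-12 weeks) or by wounds which do not heal at all".

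The study purpose in the synopsis is evidence for the "management of chronic open wounds (pressure ulcers, venous leg ulcers, diabetes-related foot ulcers") as well as dehisced wounds and closed incisions. The aim in Section 4.3 and the claims in Section 5.5 also refer to chronic wounds with no limit on age. Section 7.1 sets the quotas: "There will be a minimum of 10 of each of the following wound type; venous leg ulcers, diabetes-related foot ulcers, pressure ulcers", with the same minimum for dehisced wounds and closed incisions.

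Section 10.4.2 records "Duration of wound (weeks/months/years") at the initial assessment.

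Under Section 7.4, a consented subject found ineligible before the dressing is applied is a screen failure and is replaced. Under Section 11.2, the full analysis set (FAS) has no eligibility condition, the per-protocol (PP) set requires that the entry criteria were met, and efficacy is analysed in both.

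**The concern.** The eligibility rule limits how old a wound may be, whereas the background describes chronicity by how long a wound has already lasted. A site that follows Section 7.2 must turn away ulcers that Section 4.2 plainly calls chronic, including those that never heal. It may also enrol wounds too young to meet the Section 4.2 description.

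Three things are at stake:

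- Recruitment to the three ulcer quotas draws on a narrower pool than the purpose suggests.
- Sites that work from the ordinary sense of the term may enrol older ulcers, and those subjects then leave the PP set.
- The wound-size and infection results would describe wounds under three months old, while the clinical evaluation report they feed speaks of chronic wounds in general.

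**Working it through.** The plan gives no figure to reproduce on this point. The check sets the duration intervals side by side.

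**Inputs**
- Ceiling: under 3 months (synopsis; Section 7.2).
- Lower condition: not healing after 4 weeks of standard care (same places).
- Background floor: 6 to 12 weeks, no ceiling (Section 4.2).
- Quotas: at least 10 for each of three ulcer types, and 70 subjects in all (Section 7.1).
- Assumption: standard care starts at wound onset. The documents do not say so.

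**Steps**
1. Ceiling in weeks: 3 × 365.25 / 12 / 7 = 13.04.
2. Eligible window: 13.04 − 4 = 9.04 weeks, from week 4 to about week 13.
3. Overlap with a 6-week floor: 13.04 − 6 = 7.04 weeks, or 7.04 / 9.04 = 78% of the window.
4. Overlap with a 12-week floor: 13.04 − 12 = 1.04 weeks, or 1.04 / 9.04 = 12% of the window.
5. Eligible under Section 7.2 but short of the Section 4.2 floor: weeks 4 to 6 at the lower figure, weeks 4 to 12 at the upper.
6. Chronic under Section 4.2 but ineligible under Section 7.2: every wound of three months or more, at either figure.
7. Subjects under the rule: at least 3 × 10 = 30 of 70, or 43%. With at least 10 dehisced wounds and 10 closed incisions, the most is 70 − 20 = 50.

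**Sensitivity to the assumption.** If standard care starts *k* weeks after onset, the lower edge becomes 4 + *k* weeks and the window 9.04 − *k* weeks. At *k* = 2 the window is 7.04 weeks and lies wholly above the 6-week floor, so the young-wound mismatch in step 5 disappears at that figure. Step 6 does not depend on *k*.

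**What happens to an ulcer of three months or more**
- Rule applied: the patient is turned away at pre-screening or, once consented, is a screen failure and is replaced.
- Rule overlooked and dressing applied: the subject fails an entry criterion and is outside the PP set, but stays in the FAS given a visit after baseline.

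The protocol gives no distribution of wound age among candidates, so the share of patients excluded cannot be calculated.

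**The case against.** The strongest reply is that Section 4.2 is general background, hedged as typical, while Section 7.2 is an operational definition expressly for this study. A trial may enrol a subset. The footnote is worded identically in two places and fits with the 4-week condition. This stands in part: the two texts are not mutually exclusive, and a deliberate window of about 4 to 13 weeks is possible. But nothing explains such a window, and the purpose, aim and claims are not limited to match it.

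A reader might go further in several ways that the documents do not support:

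- **The inequality is reversed.** This is possible, but no text shows it.
- **The study was meant to cover long-standing ulcers.** No section says so. It is an inference from the unqualified purpose and from the non-healing wounds in Section 4.2.
- **The duration field contradicts the criterion.** It is a list of recording units, in a section that also serves dehisced wounds. It is weak evidence of who is eligible.
- **Every older ulcer is a protocol violation.** Normally it is a screen failure. A deviation arises only if the subject is enrolled anyway, and the FAS still retains that subject.
- **Younger wounds heal better, so results will be flattered.** The protocol does not relate healing or infection to wound age in this range.
- **The primary endpoint is compromised.** It consists of delivered pressure and absence of exudate leaks, and the sample size rests on pressure alone. Neither is linked to wound age anywhere. PP losses would reduce the number analysed in that set, but the documents give no basis for estimating how many.

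**Conclusion.** The mismatch is real and should be resolved. The synopsis and Section 7.2 exclude every ulcer of three months or more, which Section 4.2 counts as chronic, while Sections 2, 4.3 and 5.5 set no age limit. The two definitions share 7.0 weeks of a 9.0-week window at the 6-week floor and 1.0 week at the 12-week floor, assuming standard care begins at onset. The exclusion of older ulcers holds without that assumption.

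The rule governs at least 30 of 70 subjects. Its effect is on eligibility, recruitment to the ulcer quotas, PP membership, and how far the secondary wound-size and infection results can be generalised. No effect on the pressure or leak endpoint is shown, and no sample-size figure changes. Which definition was intended cannot be determined from the documents.

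**What to change.** Reconcile the synopsis, Section 4.2 and Section 7.2 under one duration rule, and state whether the 4 weeks of standard care are counted from wound onset.

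- If the direction of the limit is an error, correct it in both the synopsis and Section 7.2.
- If the window is intended, say why, and restrict the purpose and claims in Sections 2, 4.3 and 5.5 to wounds of that age.
- If older wounds are admitted, add to Section 11.6 a summary of wound-size results by baseline duration. Section 10.4.2 already collects it, but the planned wound-size summaries do not name it. If the short window is kept, this split would tell little, because each ulcer group is guaranteed only 10 subjects over about 9 weeks.

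The cost is amendment wording and, in the last case, one extra table. No new data or patients are needed.

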7.3 EXLUSION CRITERIA

Any one (1) of the following criteria will disqualify a potential subject from participation in the study:

- 1. Contraindications (per the PICO 14 IFU) or hypersensitivity to the use of the investigational product or their components (e.g. silicone adhesives and polyurethane films [direct contact with incision], acrylic adhesives [direct contact with skin], polyethylene fabrics and super-absorbent powders [polyacrylates]) within the dressing).
- 2. Subjects with extremely fragile skin who require the use of SECURA non-sting barrier skin wipes and have hypersensitivity to the ingredients in the wipes.
- 3. Participation in the treatment period of another clinical trial within thirty (30) days of operative visit or during the study.
- 4. Subjects with skin features (e.g. tattoos, skin colour, pre-existing scarring) which in the opinion of the Investigator, will interfere with the study assessments.
- 5. Patients undergoing a procedure as part of palliative care.
- 6. Subjects who have participated previously in this clinical trial and who have healed or been withdrawn.
- 7. Subjects with a history of poor compliance with medical treatment.
- 8. Malignant wounds, open abdomen wounds which have been previously managed with NPWT in the previous four weeks.
- 10. Women who are pregnant, nursing, or of child-bearing potential who are not utilizing highly effective birth control measures
- 11. Subjects with a medical or physical condition that, in the opinion of the Investigator, would preclude safe subject participation in the study.
- 12. Presence of infection as determined by the clinical signs and symptoms (International wound infection⁵⁹).
- * Please see table below for clinical symptoms of infection as determined by the International Consensus update 2016

CONFIDENTIAL AND PROPRIETARY

Study Protocol—Device	Smith-Nephew
and performance of PICO 14 in the	Number: PICO14.WND.PRO.2019.03
	Version: 2.0, 12Sep2021 Page: Page 45 of 131

7.4 SCREENING.

Participating study sites are required to document all screened subjects considered for inclusion in this study. If a subject is excluded from the study, the reasons for exclusion will be documented in the subject's source documents and noted on the Screening and Enrollment Log. All screening activities that occur prior to consent shall be referred to as pre-screening.

Part of the screening process will include documentation of women's childbearing potential. If the woman is not of childbearing potential this should be documented in the medical history (e.g., surgically postmenopausal, postmenopausal [i.e., at least one year without menses]). For women of childbearing potential, their method of birth control should be documented in the source.

A screen failure is any subject who has signed a consent form and goes on to become ineligible for the study prior to the application of the study dressing (section 7.8.1 and 7.8.2). Information must be captured in the appropriate CRFs up to the point of screen failure with the reason for screen failure specified. Screen failures will be documented in the subject's source documents and on the Trial Register. Any screen failures will be replaced.

7.5 INFORMED CONSENT.

Before conducting any study procedures or examinations, the purpose and nature of the study will be explained to the subject in their native language. The subject, or their legally authorized representative, will then read, sign, and personally date the IRB/IEC approved informed consent document(s) (see below for difficulties with reading and writing). Additionally, the individual who obtains consent from the subject will sign and date the informed consent document. A copy of the signed informed consent documentation will be provided to the subject, a copy will be placed in the subject's medical record, with the original filed in the ISF.

If the subject is unable to read, the informed consent document and associated study information may be read aloud to the subject in the presence of an impartial witness. If possible the subject shall sign and personally date the Informed Consent Form (ICF). Where this is not possible, due to difficulties in writing, the subject shall provide verbal consent to participate in the study. The

CONFIDENTIAL AND PROPRIETARY

Study Protocol—Device	Smith-Nephew
and performance of PICO 14 in the	Number: PICO14.WND.PRO.2019.03
	Version: 2.0, 12Sep2021
	Page: Page 46 of 131

witness shall then personally sign and date the informed consent form, attesting that the information was accurately explained and that the informed consent was freely given.

All subjects will be given time to consider participation following the explanation of the study/reading of the patient information sheet. At least 24 hours will be needed before patient can consent to study. No true emergency cases (where the subject is unconscious or does not have time to consider the study) will be consented for this study.

If the subject is unable to read, the informed consent document and associated study information may be read aloud to the subject in the presence of an impartial witness. If possible, the subject shall sign and personally date the Informed Consent Form (ICF). Where this is not possible, due to difficulties in writing, the subject shall provide verbal consent to participate in the study. The witness shall then personally sign and date the informed consent form, attesting that the information was accurately explained and that the informed consent was freely given.

Due to COVID-19 pandemic verbal consenting might be required by sites to achieve consent from participants who are unable to attend at the time of consent. Process for this will involve, site to provide PIS and full information on the study at least 24 hours prior to the Verbal call and consent.

Verbal consent will be sought and the consenter will date and sign the ICF on the participant behalf, the participant will be screened thereafter and once in clinic they will be asked to sign and date the ICF personally. In the case of emergency situations, the ICF may be obtained and information on the clinical study may be given after the decision to include the subject in the clinical investigation if the following situations apply:

Subject is unable to consent due to the form of wound (dehished wound only) in which
wound becomes opened and dehished and requires urgent treatment within hours of
the wound being diagnosed as such by Investigator. Due to the time sensitivity of this
cohort of participants, the risk is that this cohort might not be included in study if
emergency consenting is not allowed.

ICF will be obtained from the legally designated representative as soon as possible. In addition, informed consent to continue participation in the clinical investigation will be obtained from the subject as soon as the subject is capable to give informed consent.

CONFIDENTIAL AND PROPRIETARY

Study Protocol—Device	Smith-Nephew
and performance of PICO 14 in the	Number: PICO14.WND.PRO.2019.03 Version: 2.0, 12Sep2021
management of acute and chronic wounds	Page: Page 47 of 131

If the subject or the legally designated representative (if applicable) does not give consent, the subject or legally designated representative will be informed of the right to object to the use of data obtained from the clinical investigation.

If new information becomes available during the course of the study that can significantly affect a subject's future health and medical care, Smith + Nephew will ensure that information shall be provided to the subject(s) affected in written form and if relevant, all affected subjects shall be asked to confirm their continuing consent in writing.

7.6 ENROLLMENT.

Enrolment in this study shall occur at the point the consent process has been completed and study number is allocated to the subject.

7.7 LOST TO FOLLOW-UP.

A subject will be considered lost to follow-up if he/she does not appear for the scheduled study visit for 2 consecutive visits and does not return for a final visit, and study personnel are unable to contact the subject.

Some actively enrolled subjects will not return for follow-up exams on time. Study personnel must make a reasonable effort to contact the subject and document the following contact attempts before declaring a subject to be lost to follow-up: the subject has been contacted according to the site's policies, but no fewer than two documented phone contacts and one certified letter without response. Copies of all attempts to reach the subjects by mail or email and/or the attempts to contact the subject via other means should be documented, and that documentation should be kept with the subject's source documents.

CONFIDENTIAL AND PROPRIETARY

Study Protocol—Device	Smith-Nephew
and performance of PICO 14 in the	Number: PICO14.WND.PRO.2019.03
	Version: 2.0, 12Sep2021
	Page: Page 48 of 131

7.8 WITHDRAWAL.

7.8.1 WITHDRAWAL OF TREATMENT.

Subjects may be withdrawn early from study treatment for the following reasons:

- Subject does not return following treatment (and pump is lost).
- Treatment is prematurely ended for any reason (i.e. due to removal of the system by the subject, failure of the pump, dressing falls off, seal can no longer be established).
- Treatment is disrupted for longer than 24 hours (i.e. airtight seal was disrupted and was not re-established with a 24 hour time period).
- At the discretion of the Investigator due to:
 - A change in treatment is clinically warranted (to include further treatment following
 14 day therapy)/28 day therapy for chronic wounds and dehisced surgical wounds.
 - An adverse event or device deficiency.
 - Any other significant reason identified by the Investigator.

7.8.2 WITHDRAWAL FROM STUDY.

The Investigator may withdraw subjects from the study for many reasons, including but not limited to the following:

- subject noncompliance (e.g., did not follow instructions, took disallowed medications)
- subject lost to follow-up
- if the Investigator or the Sponsor stops the study for any reason and decides to withdraw subject(s) from the study
- concurrent illness

CONFIDENTIAL AND PROPRIETARY

Study Protocol—Device	Smith-Nephew
and performance of PICO 14 in the	Number: PICO14.WND.PRO.2019.03
	Version: 2.0, 12Sep2021
	Page: Page 49 of 131

- Adverse Events/Adverse Device Effects
- any other significant reason identified by the Investigator

For each case, information will be obtained in the source document and the Case Report Form (CRF), detailing circumstances leading to the withdrawal.

Subjects who are treated for with surgery that ends with a closed incision and subjects who drop out, or are withdrawn, will not be re-entered into the study at a later date.

7.8.3 SUBJECT'S WITHDRAWAL OF CONSENT TO PARTICIPATE IN STUDY.

Study participation is voluntary, and subjects may withdraw at any point during the study without giving their reason for doing so. Where subjects withdraw consent, the Investigator should make a reasonable effort to ascertain the reason(s), while fully respecting the subject's privacy. The reason for withdrawal will be recorded in the CRF and source documents.

7.8.4 USE OF DATA FOLLOWING WITHDRAWAL.

In cases where the subject withdraws consent, the data collected up to the point of withdrawal may be used, but no additional data for that subject may be collected.

